**D.4d. Quantitative evaluation:**

**D.4d1. Cohort identification:** To assess impact of IF efforts, we will identify a cohort of at-risk patients—those who have OUD but are not prescribed MOUD—to track their outcomes over time. Methods to identify at-risk patients will be harmonized across all implementation sites. These will include use of available data in the Corporate Data Warehouse (CDW), including medication/pharmacy records (inpatient and outpatient), toxicology screen results, primary care and mental health care utilization, inpatient admissions, comorbidity data, recent treatment and service use such as alternative pain treatments for the subgroup of MOUD patients with pain, and other information to determine at-risk Veterans appropriate for referral for MOUD. We will compare outcomes at each implementation site during the post-implementation period to outcomes prior to implementation, using each site as their own control. Each site will have a defined implementation start date and an implementation start-up period of 3-months in which outcomes will not be attributed to either the pre- or post-implementation period. For sites that have booster or additional implementation efforts, additional start dates of those efforts will be tracked. Harmonization of definitions for at-risk Veterans will also facilitate comparing sites across VHA not participating in MOUD-related implementation activities to examine secular trends and to rapidly identify targets for expanding the implementation efforts for MOUD referral in additional VISNs. A person-years approach will be used as Veterans may be at-risk and eligible for referral for MOUD at multiple time points during the three-year project.

**D.4d2. Implementation/clinical outcomes:** The Quantitative/Economic Core will work with the Implementation Core on two primary areas: (1) ensuring accuracy and consistency of assessments of RE-AIM

outcomes across CONDUIT, with the Quantitative/Economic Core focused on Reach, Effectiveness, and Adoption; and (2) assisting in tracking and assessing frequency and duration of IF activities (e.g., logs of time related to implementation efforts that includes phone calls, meetings, education) across EF teams so that costs can be assigned to implementation efforts (**Table 5**). **Reach**: The primary reach outcome is the use of MOUD among at-risk individuals. At each implementation site we will identify at-risk individuals during the pre- and post-implementation periods, using modified criteria from the MOUD dashboard. Using the cohort definitions described above, each at-risk Veteran will be assigned an index date and at-risk person-years will be determined for both pre- and post-implementation periods as appropriate. The outcome will be calculated based on filling a qualifying prescription for buprenorphine or naltrexone. We note that this outcome is similar to the SCOUTT evaluation, however, the SCOUTT evaluation focuses on individual provider prescribing practices because providers were the focus of the intervention. In CONDUIT, any fill of buprenorphine or naltrexone will be counted because the focus on the implementation efforts are on the entire site, not individual provider practices. **Effectiveness**: Our primary effectiveness outcome will be the number of at-risk Veterans who participate in a full course of MOUD. This analysis will be similar to the Reach analysis, but will focus on the date of completing a full course of MOUD. Secondary outcomes will include rates of hospitalizations and ED visits related to OUD/SUD for Veterans who utilized MOUD compared to Veterans who do not use MOUD during the pre- and post-implementation period. Using a person-years approach we will identify at-risk individuals and determine the relevant time that they are at risk of potential adverse events. Hospitalization and ED visits with a primary or secondary diagnosis code of OUD/SUD will be identified using established methods, and will be guided by SCOUTT evaluation. We also propose examining the effect of implementation on a) total opioid doses; b) receipt of overlapping opioid-sedative prescriptions, and c) opioid-related or other

**Table 5.** Outcomes Mapped to RE-AIM Constructs

RE-AIM Construct	Primary Outcome(s)	Secondary Outcomes
Reach	Number of patients with OUD initiating MOUD during the implementation period in implementation sites 	
Effectiveness	Number of patients with OUD retained on MOUD at 90 days and 180 days during the implementation period (i.e. treatment retention) 	
 
▪ Hospitalizations and ED visits related to OUD post-implementation
 
▪ Opioid-related or other drug overdoses in patients with OUD post-implementation
 
▪ Opioid dose for patients on LTOT post-implementation
 
▪ Concomitant opioid-sedative prescriptions post-implementation
 

Adoption	Number of providers (and/or clinics) providing MOUD post-implementation, stratified by type of provider, clinical setting 	Number of VISTA x-waivered providers post-implementation 
Implementation	
 
▪ Facilitators and barriers to implementation
 
▪ Fidelity, as measured by frequency and duration of Implementation Facilitation strategies and other implementation strategies
 
▪ Cost of implementation
 
	Variation in facility-level use of implementation strategies over time
Maintenance	
 
▪ Summary of facilitators and barriers at implementation clinics 6 months post-implementation
 
▪ Elements of program maintained, including adaptations
 
▪ Number of VISTA x-waivered and prescribing providers 6-month period post-implementation
 
	Number of OUD patients receiving MOUD 12-24 months after implementation

**Data source:** CDW; Semi-structured interviews; REDCap facilitation tracking logs; REDCap survey of ERIC strategies.

drug overdoses. Coding strategies will be adapted as necessary to address Cerner adoption and CHOICE and MISSION use of community care records. **Adoption:** Outcomes focused on provider adoption of MOUD will be assessed. For each implementation site we will identify providers and assess the proportion of those providers who provide MOUD or who are credentialed to provide MOUD (VISTA X-waivered providers). Changes in these proportions between the pre- and post-implementation periods will be assessed as an indicator of implementation success.

**D.4d3. Analytic approaches:** Our non-randomized evaluation design is necessary because randomization was not possible due to our partnership with VISN leadership and outreach efforts for individual site participation. A key goal is to demonstrate to VISN and facility leadership the value of implementation; therefore, we will estimate implementation outcomes for each of our individual sites and pool implementation sites as appropriate. This will allow us to provide descriptive quantitative information about individual implementation efforts to be combined with qualitative findings about implementation success. Although these analyses will allow for some comparison of effectiveness across individual team efforts, we do not propose formal direct comparisons of teams. There are several statistical limitations to the non-randomized evaluation design that we will address through pragmatic approaches. To account for secular trends in increased use of MOUD that may not be due to our implementation efforts, we will track other related implementation efforts such as initiation of additional SCOUTT efforts, and monitor national dashboards to generate a secular rate among non-intervention sites. We will use this secular rate and test to determine if CONDUIT activities increase use of MOUD above this rate, rather than a null hypothesis of 0. Because we are calculating outcomes for each of the individual sites, the risk of a spurious finding due to multiple testing is possible. We will use caution when interpreting any moderate p-values (e.g. 0.01 to 0.05) as significant. For ease in reporting to VISN and site leadership, we will utilize direct pre- and post-implementation period comparisons. Additional multivariate adjusted analysis using time-to-event semi-parametric methods will also be explored. These models will focus on initiation of MOUD treatment, and will allow for examining clinical and demographic characteristics, including time from initial OUD diagnosis.

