**VISN19:** The VISN19 PII team has delivered three buprenorphine waiver trainings in primary care settings to expand the workforce of prescribers qualified to prescribe buprenorphine. As of May 2019, there are 59 prescribers in the VA Eastern Colorado Health Care System (ECHCS) with a buprenorphine waiver with 7 PCPs and 8 Internal Medicine residents completing waiver training during Phase 1. In the VA Salt Lake City Healthcare System, there are 78 prescribers with a buprenorphine waiver. They have met with VISN leadership on a quarterly basis during Phase 1 to discuss progress and barriers. In collaboration with the MAT-VA Initiative, they have led monthly webinars on OUD diagnosis and treatment for a national audience. They

have also engaged Veterans, completing 10 semi-structured interviews of Veterans with OUD at VA Salt Lake City to understand perspective on primary care-based OUD treatment.

**VISN22:** The VISN22 PII team conducted key stakeholder interviews among PCPs, nurses, pain providers, addiction psychiatrists, and Veterans and analyzed site-specific baseline data on process and outcome measures for our two VISN22 pilot sites. They led three waiver trainings for a total of 46 providers at 2 sites. They are developing multiple products to support expanded implementation: a PowerPoint presentation for PCPs on how to recognize and treat OUD; a coding “cheat sheet” for PCPs and psychiatrists to use in managing patients with OUD (including ICD-10 and CPT codes); a training pathway for X-waivered prescribers to increase confidence in prescribing buprenorphine.

**VISN23:** The VISN23 PII team developed an opioid management guide to promote changes in inpatient opioid prescribing practices and improve recognition and management of OUD. They developed an order set to facilitate use of non-pharmacologic pain treatment options available in the hospital. Based on a survey of nationally available resources and guides for MOUD, they drafted a VHA-specific toolkit for improving recognition and management of OUD in the inpatient setting. One hospitalist prescriber has obtained an X-waiver during Phase 1. Finally, they identified synergies with colleagues expanding MOUD to Emergency Department settings where shared implementation strategies will be beneficial.

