### **D.3b. Brief summaries of CONDUIT programs by clinical setting:**

**Primary care:** Buprenorphine delivered in primary care is associated with decreased opioid use, higher quality of care, and improved quality of life. Thus, evidence-based models of primary care-based OUD treatment, namely the Medical Management model and the Nurse Care Management model, are the focus of CONDUIT implementation in primary care settings. In this program, the EF team works collaboratively with internal facilitation teams to expand the availability of MOUD in VHA primary care settings by increasing the number of providers/teams prepared to initiate and manage evidence-based MOUD.

**Specialty care:** This program prioritizes patients on LTOT for chronic pain, as many in this sub-population already have OUD, are at high risk for developing it, or may be experiencing negligible benefit. Consistent with VA/DoD guidelines and a mandate from the Comprehensive Addiction and Recovery Act of 2016, we developed a multi-disciplinary clinical program—the Opioid Reassessment Clinic (ORC)—that assesses benefits and harms, seamlessly initiates MOUD when OUD is diagnosed, and ensures access to evidence-based non-opioid treatments for pain.

**Acute care (inpatient / emergency department):** This program capitalizes on ED visits or hospitalization as critical intervention windows by engaging ED physicians and hospitalists to reduce opioid overprescribing and increase uptake of MOUD while reaching patients at high-risk due to medical comorbidities. We integrate evidence-based and established consensus approaches to opioid prescribing, use of non-pharmacologic pain treatment, and diagnosis and treatment of OUD in hospitalized patients, into a coherent approach that can be adapted to medical centers with and without specialty pain or addiction medicine services.

**Telehealth:** While there is an inadequate number of providers in rural areas certified and/or trained to provide MOUD, telemedicine has been found to be as effective as in-person visits for treating a range of mental illnesses, and for prescribing buprenorphine and other MOUD.

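### Facilitation changes who enters the at-risk cohort, so the pre/post Reach rate can be biased in either direction and can stay flat or fall while more Veterans are treated

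*Combined protocol and SAP*

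**What the plan says.** Section D.4d1 defines at-risk patients as "those who have OUD but are not prescribed MOUD". They are found from Corporate Data Warehouse records: pharmacy, toxicology, utilization, admissions, comorbidity and "other information to determine at-risk Veterans appropriate for referral for MOUD". Each site is its own control, and a Veteran may be at risk more than once.

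Section D.4d2 states: "The primary reach outcome is the use of MOUD among at-risk individuals". On timing it says "we will identify at-risk individuals during the pre- and post-implementation periods, using modified criteria from the MOUD dashboard", and on the denominator "each at-risk Veteran will be assigned an index date and at-risk person-years will be determined". Any buprenorphine or naltrexone fill counts. Neither section defines the index date, a minimum MOUD-free interval, or the handling of a fill on the day of diagnosis.

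Table 5 words the primary Reach outcome differently: "Number of patients with OUD initiating MOUD during the implementation period in implementation sites". That is a count.

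On what is being implemented, D.3b says the specialty clinic "seamlessly initiates MOUD when OUD is diagnosed", and its acute-care paragraph includes diagnosing OUD in hospitalized patients. The VISN23 paragraph of C.1 describes Phase 1 work to "improve recognition and management of OUD". Section A treats better diagnosis as a goal alongside better treatment.

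**The concern.** A Veteran enters the cohort by meeting two conditions: having OUD and not being on MOUD. The programs act on both. Better recognition brings in Veterans who would not have been identified in the pre-period. Starting MOUD at diagnosis shortens or removes the untreated interval that qualifies a Veteran for entry. Because the post-period cohort is drawn after facilitation has begun, the pre and post rates describe populations selected differently.

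At stake is the main pre/post comparison reported to VISN and site leadership, most of all in specialty and acute care. The text also defines the primary Effectiveness outcome among at-risk Veterans, and the models in D.5g use person-years as the unit of analysis. A distorted initiation estimate could therefore carry into those results and into the cost per additional Veteran initiating MOUD (D.5b).

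**Working it through.** **The plan's own figures.** The plan gives no figure for this effect. The only calculation on the at-risk cohort is Table 6. With two-sided alpha 0.05 (assumed; not stated) and power 0.80, (1.960 + 0.842)/√n for n = 50, 75, 200, 750 gives 0.396, 0.323, 0.198, 0.102. This matches the printed 0.40, 0.32, 0.20, 0.10. Table 6 is not in dispute; it takes n as given and does not address who enters.

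**Inputs for the illustration, all assumed.** N = 200 Veterans in the cohort without extra diagnoses; p0 = 20% of them start MOUD; E = extra diagnoses due to facilitation; s = share of E started at the same visit and so, on the literal reading, outside the cohort; q = start probability of the rest. Follow-up per person is taken as equal at first.

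**Extra diagnoses.** Let L = E(1 − s).

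- Cohort rate = (N·p0 + L·q)/(N + L)
- Change from p0 = L(q − p0)/(N + L)
- Veterans treated = N·p0 + L·q + E·s

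The rate falls if q < p0, is flat if q = p0, and rises if q > p0. With E = 50 (25% more) and 40 treated before:

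| Case | s | q | Treated after | Rate in plan's cohort | Rate with same-visit starts counted |
|---|---|---|---|---|---|
| A | 0.5 | 10% | 40 + 2.5 + 25 = 67.5 | 42.5/225 = 18.9% | 67.5/250 = 27.0% |
| B | 0.5 | 20% | 40 + 5 + 25 = 70 | 45/225 = 20.0% | 70/250 = 28.0% |
| C | 0 | 10% | 40 + 5 = 45 | 45/250 = 18.0% | 18.0% |
| D | 0.5 | 30% | 40 + 7.5 + 25 = 72.5 | 47.5/225 = 21.1% | 72.5/250 = 29.0% |

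Case C shows that counting same-visit starts does not cure enlargement of the cohort. Over a denominator that diagnosis leaves unchanged, the initiation rate would rise in proportion to the number treated: 45/40 = 1.125 times in case C, 67.5/40 = 1.69 times in case A.

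**Range.** Take E from 10% to 50% of N, s from 0 to 0.5, and q from 0.5 to 1.5 times p0.

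- At p0 = 20%, treated goes from 40 to between 42 and 105; the cohort rate lies between 16.7% and 23.3%.
- At p0 = 23.7% (the national figure in Table 2, a share receiving MOUD and not an initiation rate), treated goes from 47.4 to between 49.8 and 115.2; the rate lies between 19.8% and 27.6%.

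The number treated rises in every scenario; the rate does not.

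**Same-visit starts without extra diagnoses.** Move m Veterans out of the cohort, of whom a fraction r would have started later anyway. The rate becomes (N·p0 − m·r)/(N − m), which is below p0 only if r > p0. With 60 of the 200 newly diagnosed and 20% of them started at the visit, m = 12.

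- r = 0.7: (40 − 8.4)/188 = 16.8%, with 31.6 + 12 = 43.6 treated.
- r = 0: 40/188 = 21.3%, with 40 + 12 = 52 treated.

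**Unequal person-time.** If the 50 extra Veterans in case C average half a period at risk, the rate is 45/(200 + 25) = 20.0 per 100 person-periods: flat instead of falling, with 45 treated instead of 40. The condition on q then applies to starts per unit of at-risk time.

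**Rate and count in the plan's own data.** In Table 1 Manchester goes from 153 (22%) to 139 (46%). The implied denominators are 153/0.22 ≈ 695 and 139/0.46 ≈ 302, so the rate doubled while the count fell. These are dashboard totals, not the at-risk cohort, and Table 2 gives 32.0% for the same site and quarter from another dashboard. They show only that the two measures can part.

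**The case against.** Several points on the other side are sound.

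- **Table 5.** Its Reach measure is a count of patients with OUD who initiate MOUD. Extra diagnoses cannot dilute it, and it would include same-visit starters. That stands. But it has no denominator, can rise through more diagnosis alone, and is not the measure described in the D.4d2 text.
- **Coding.** A reader might infer that entry requires an OUD diagnosis code. The documents do not say so: D.4d1 lists wider data, and D.4d2 refers to modified dashboard criteria that are not set out.
- **Same-visit starters.** A reader might infer that they are excluded. That follows only from a literal reading of the definition. If the index date is the diagnosis date and a same-day fill counts, they are in the numerator. The rule is undefined; exclusion is not shown.
- **Direction.** A reader might infer that Reach will be understated. The algebra does not support a fixed direction, and unequal person-time can turn a fall into no change.
- **Evidence on recognition.** The C.1 wording describes a Phase 1 guide in VISN23, which has one site in Table 2. The acute-care and specialty text in D.3b is the broader support.

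The planned safeguards help less than they seem to. The secular rate in D.4d3 comes from sites without this facilitation, so it cannot cancel a facilitation-driven change in entry. Using each site as its own control is the very comparison affected. The time-by-implementation interaction in D.5g targets secular trend. The three-month start-up gap removes calendar time, not later changes in recognition. The time-to-event models in D.4d3 may include time from initial OUD diagnosis, which bears on the mix of new and established patients, but they are only to be explored.

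**Conclusion.** The concern holds in a limited form. The Reach rate in the text has a denominator that facilitation can change, and nothing in the plan removes the resulting bias. The rate can stay flat or fall while more Veterans are treated, and it can also rise through selection.

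The documents give no initiation rate, no expected change in diagnoses and no share of same-visit starts, so the size is unknown. Under the assumed ranges at p0 = 20%, the cohort rate runs from 3.3 points below to 3.3 points above its starting value while the number treated rises by 5% (42/40) to 163% (105/40). Those figures rest on equal follow-up and on same-visit starters being outside the cohort; they show what is possible and are not a forecast.

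**What to change.** 1. **Index date.** Set it at the first qualifying OUD record in the period, or at re-entry to untreated status so that the multiple at-risk episodes in D.4d1 are kept. Count fills from day 0. A day-0 start adds an event with almost no person-time, so the person-years rate and the time-to-event models need a stated convention for it.
2. **Second denominator.** Beside the at-risk rate, report and test MOUD initiations per 1,000 Veterans in care at the site, pre versus post and against the same rate at non-intervention sites. Alternatively, run a sensitivity analysis in a cohort fixed before facilitation; this is free of changes in entry but is silent on Veterans first recognised later.
3. **Interpretation.** Report both measures and read divergence as a change in case finding. Do not require them to agree in direction: in case C that rule would block a real gain. Reconcile the D.4d2 text with Table 5 by stating which Reach measure is primary.

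The cost is a cohort rule and one more Corporate Data Warehouse denominator. The population rate is small in absolute terms. As a rough guide from Table 2, 1.51% OUD prevalence times 23.7% on MOUD is 0.36%, or about 3.6 per 1,000 receiving MOUD (assuming the prevalence is per Veteran in care). That is a prevalence, not an initiation rate. Small sites will therefore need pooling, as the plan already foresees.

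### Table 5 and section D.4d2 give different condition sets for the hospital/ED outcome, and counting secondary codes leaves its pre/post comparison open to program-driven coding change

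*Combined protocol and SAP*

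**What the plan says.** Section D.4d2 gives as a secondary effectiveness outcome "rates of hospitalizations and ED visits related to OUD/SUD for Veterans who utilized MOUD compared to Veterans who do not use MOUD", in both the pre- and post-implementation periods. The counting rule follows: "Hospitalization and ED visits with a primary or secondary diagnosis code of OUD/SUD will be identified using established methods". For any further detail the section points only to the evaluation of another initiative, SCOUTT. There is no code list and no rule for deciding when a visit is due to OUD.

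Table 5 enters the outcome as "Hospitalizations and ED visits related to OUD post-implementation". It does not mention other substance use disorders or code position. It lists drug overdoses as a separate secondary outcome.

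The cohort in D.4d1 is "those who have OUD but are not prescribed MOUD". It is found from Corporate Data Warehouse (CDW) records that include admissions and comorbidity data. The rate basis is person-time: "Using a person-years approach we will identify at-risk individuals and determine the relevant time that they are at risk". Sites are compared before and after implementation, "using each site as their own control". In D.3b the acute-care program works with ED physicians and hospitalists and includes "diagnosis and treatment of OUD in hospitalized patients".

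**The concern.** There are two linked problems.

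First, an alcohol or stimulant admission is an event under D.4d2 but not under Table 5. If this is not settled before data are seen, the choice of definition can be made afterwards.

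Second, everyone in the cohort has OUD. Once a secondary code is enough, whether an admission for something else counts depends on whether staff record OUD as a comorbidity. The acute-care program aims to make hospital staff more likely to recognize OUD. The program can therefore change the measure without changing health. A site could appear to have more OUD-related admissions because its staff recognized OUD better, or a real fall could be hidden. Section D.4d3 plans direct pre/post comparisons for VISN and site leadership, which is where this would show without adjustment.

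**Working it through.** **1. The two definitions side by side.**

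| Feature | Table 5 | D.4d2 |
|---|---|---|
| Conditions | OUD | OUD or other SUD |
| Code position | not stated | primary or secondary |
| Contrast | not stated | MOUD users vs non-users, both periods |

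The conditions conflict. On code position, D.4d2 can be read as the operational rule for a short table label.

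**2. Do the planned safeguards cover program-driven coding?**
- The secular-rate test in D.4d3 is described for MOUD use, not for admissions or coding.
- The coding provision in D.4d2 concerns the change of record system and community care records.
- The time-by-implementation interaction in D.5g is meant to separate secular trends. Coding change caused by facilitation starts with implementation, so the model would credit it to implementation.

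None of the three addresses it.

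**3. Illustration of size.** The plan states no rate, coded share or power for this outcome, so there is no figure to reproduce. All inputs here are assumptions. Let f be the share of admissions truly caused by OUD/SUD (taken as always coded), and s the chance that any other admission carries a secondary OUD/SUD code. The flagged share is

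p = f + (1 − f)s.

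Example with f = 0.3 and s rising from 0.2 to 0.3:
- Before: 0.3 + 0.7 × 0.2 = 0.44.
- After, with no true change: 0.3 + 0.7 × 0.3 = 0.51. Ratio 0.51/0.44 = 1.16.
- After, with a true 20% fall in caused admissions: (0.8 × 0.3 + 0.7 × 0.3)/0.44 = 0.45/0.44 = 1.02.
- The same fall with coding unchanged: (0.24 + 0.14)/0.44 = 0.86.

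| f | s before → after | p before → after, no true change | Ratio, no true change | Ratio, true 20% fall |
|---|---|---|---|---|
| 0.1 | 0.2 → 0.3 | 0.28 → 0.37 | 1.32 | 1.25 |
| 0.3 | 0.2 → 0.3 | 0.44 → 0.51 | 1.16 | 1.02 |
| 0.3 | 0.4 → 0.5 | 0.58 → 0.65 | 1.12 | 1.02 |
| 0.3 | 0.6 → 0.7 | 0.72 → 0.79 | 1.10 | 1.01 |
| 0.5 | 0.6 → 0.7 | 0.80 → 0.85 | 1.06 | 0.94 |

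Over f = 0.1 to 0.5 and the three 10-point shifts, the event count rises 6% to 32% with no true change.

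**4. The denominator.** Better recognition can also bring new patients into the cohort. If person-years grow by a fraction g and the new members have r times the event rate of existing members, the rate is multiplied by (1 + gr)/(1 + g).
- g = 0.1, r = 0.5: 1.05/1.10 = 0.955.
- g = 0.3, r = 0.25: 1.075/1.30 = 0.827.

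Combining extremes gives 1.062 × 0.827 = 0.88 and 1.321 × 0.955 = 1.26. The rate can move either way. If r = 1, there is no dilution.

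**5. What an all-cause measure would show.** It does not depend on s. At f = 0.3, a 20% fall in caused admissions is a 0.3 × 0.2 = 6% fall in all admissions: free of event coding, but diluted.

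**The case against.** The strongest reply is that Table 5 is a one-line map, D.4d2 supplies the rule, and the algorithm is deferred to established methods and the SCOUTT evaluation, which may narrow it. This disposes of any conflict on code position. It does not reconcile OUD with OUD/SUD, and any narrowing rule elsewhere cannot be seen in these documents.

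The contrast named in D.4d2 is MOUD users against non-users. Coding drift shared by both groups would largely cancel there. That stands, and it limits the concern mainly to the pre/post comparison, which D.4d1 and D.4d3 do plan. Differential coding is possible, since a MOUD prescription makes OUD visible in the chart, but that is inference.

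The mechanism is also narrower than facilitation as a whole. Only the acute-care program, one of four settings, bears directly on hospital and ED recording, and D.3b speaks of diagnosis, not coding practice. The Phase 1 coding aid described in C.1 was for primary care providers and psychiatrists, so it is weak support. The acute-care link is enough to raise the issue, but not to show that coding will change.

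Finally, a primary-position rule has its own cost. It misses OUD-related admissions with another principal diagnosis, and assignment of a primary code can itself shift with training. That is a fair reason to use it as a sensitivity analysis and not to impose it as the main definition.

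**Conclusion.** The point holds as a minor one on a secondary outcome. The condition sets conflict, and the pre/post comparison under the secondary-code rule is sensitive to coding change that the program may cause and no described safeguard covers. The size and net direction are unknown. The 6% to 32% rise in event count and the 0.83 to 0.96 rate multiplier rest wholly on assumed values.

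A reader might infer three stronger things that the documents do not support:
- **That the D.4d2 rule flags most admissions.** Passing 50% needs s above (0.5 − f)/(1 − f), which is 0.44 at f = 0.1 and 0.29 at f = 0.3. At s = 0.2 the flagged share is 28% to 44% for f = 0.1 to 0.3. No document figure settles it.
- **That the outcome must rise with better coding.** This is sound for the count, but not for a person-year rate whose denominator may grow as well.
- **That a primary-diagnosis definition including opioid poisoning would match Table 5.** Table 5 sets no position rule and keeps overdoses as their own outcome, so this would be a third definition.

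**What to change.** - Choose one condition set, OUD or OUD/SUD, and use it in both D.4d2 and Table 5, with a code list fixed before outcome data are examined.
- Keep the primary-or-secondary rule if wanted, and add a primary-position version as a sensitivity analysis.
- Report all-cause hospitalizations and ED visits beside it for the same cohort and periods.
- State that a pre/post change in the coded outcome will not be attributed to implementation unless these analyses agree, and say in advance what agreement means. Direction is a more reasonable test than equal size, given the dilution of the all-cause measure.
- Keep overdoses as their own Table 5 outcome.

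The cost is a wording change, a code list and one or two extra CDW analyses. The primary-position version will have fewer events. The all-cause measure is less specific, and its rate can still shift if better recognition changes who is in the cohort.
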